#### I. Background, Rationale and Context

Pregnancy and the peripartum period can function as a "stress test" for future development of cardiometabolic disease, with and gestational diabetes (GDM) and excessive gestational weight gain (GWG) portending worse outcomes later in a mother's life. The prevalence of both conditions continues to increase with the obesity epidemic, highlighting the urgent need for successful interventions to reverse maternal weight gain and promote normoglycemia. The early postpartum period provides a critical opportunity to address dietary behaviors that underlie both weight and dysglycemia. Postpartum medically-tailored meal (MTM) delivery is a novel intervention approach that may allow for improved glycemic control and weight loss in a traditionally hard-to-engage patient population. There is currently no available data on the cost, feasibility, or effectiveness of providing MTM to postpartum women.

A. GDM Plus Excess GWG Increases Risk of Adverse Maternal & Child Health Outcomes Incidence of GDM has substantially increased over the past two decades, and there is a need for interventions to reduce its long-term health impacts for mother and baby. Excess retained weight after pregnancy, impacting up to 80% of women, has important health consequences including development of Type 2 Diabetes Mellitus. GDM and gestational weight retention confer higher risk of complications in subsequent pregnancies and cardiovascular disease in the future.

B. The Postpartum Period: A Opportunity to Improve Maternal Metabolic Health Most cardiometabolic perturbations from pregnancy will either resolve or persist within 12 weeks after delivery. Further, the first 6 months after a baby is born are generally the period of most rapid weight loss for new mothers. Weight plateau and even regain typically occur by 12 months postpartum, with consequences for short and long-term glycemic control. Despite the opportunity to improve women's cardiometabolic health trajectories during the early postpartum period, many aspects of traditional weight loss and glycemic control interventions, such as intensive in-person visits and meal planning/preparation are quite difficult to implement and sustain while caring for a newborn infant. Attendance rates at postpartum clinical visits are low,  only 50% for Medicaid patients,  exemplifying the fact that new mothers have limited bandwidth for self-care activities. Postpartum dysglycemia & weight retention pose both an opportunity and a challenge for primary and secondary prevention of obstetric and cardiometabolic outcomes in women.

C. MTM programs are promising for treating Type 2 Diabetes, but there has been little uptake in practice MTMs are designed with nutritional content (caloric density, macronutrient breakdown, and other features) tailored to a specific chronic disease state, and typically operationalized by community-partners experienced in food preparation and delivery at the request of health systems or payers. Intervention studies using MTM to treat diet-related disease have shown great promise, especially for Type 2 Diabetes Mellitus where initial studies have found that MTM have been effective in improving diet quality and glycemic control. Despite growing evidence that MTM programs can improve health and decrease medical care costs, few of them have been translated from research into routine clinical practice, likely due to the high cost. Where MTM programs are available, they are often restricted to short periods of time despite the chronic nature of the diseases they are intended to treat. Such high costs are not viewed as sustainable for long-term chronic disease management by health systems or payers. To our knowledge, MTM programs have not been used for primary prevention. Use of MTM for a time-limited but critical period, such as the first 3 months postpartum, may have greater translational potential among health systems & payers.

#### II. **Objectives**

The purpose of this proposal is to test the feasibility of providing medically tailored meals for postpartum women who had gestational diabetes and gestational weight gain that exceeds the IOM guidelines. The first objective is to understand the **feasibility** (n/% of meals successfully ordered & delivered, program cost per participant, and completion rate of CGM data collection) and **acceptability** (using participant surveys and interviews with key stakeholders) of the intervention and outcome measures. The second objective is to explore the preliminary **effectiveness** of the program, via 3-month changes in CGM markers of dysglycemia (primary) as well as: maternal diet quality, maternal weight and infant weight change, initiation and maintenance of breastfeeding, household food insecurity, and validated measures of financial and overall stress (exploratory).

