#### E. Screening and Enrollment

We will generate weekly datasets using the Clarity reporting relational database in WakeOne to identify potentially eligible women within the electronic health record (EHR). The EHR data pulls will identify women, age 18 years or older, in their third trimester of pregnancy seen for obstetric care in a WFBH clinic in the past week who had a diagnosis of GDM with excessive GWG, and for whom English is the documented primary language. Datasets of up to 50 women who meet these criteria will be output weekly to a secure folder on the PHS network which only IRB-approved study staff may access. Datasets will also include patient name, age, MRN, expected delivery date, pre-gravid height and weight (to calculate BMI), current weight, diagnosis of GDM, and OGTT results. Research staff will then access individual EHR data to identify contact information and will place a telephone call to potential participants to discuss the study and to assess additional eligibility criteria. As we anticipate that some women who meet eligibility criteria may not appear in these datasets until very close to their expected delivery date and may not be reached for recruitment pre-partum, we will also attempt to contact women who appear in the dataset who have recently given birth (within the past 14 days). Additionally, a physician investigator will review diagnostic codes associated with recent encounters for all potential participants to identify any potential diagnoses or health conditions that may make participation unsafe or increase risk, including diagnosis of Type 1 or Type 2 diabetes pre-pregnancy, cardiovascular disease, essential hypertension, and dyslipidemia.

Potential participants who 1) satisfy the inclusion/exclusion criteria previously described, and 2) indicate that they are willing to provide written informed consent will be invited to complete a virtual baseline visit and be enrolled in the study. Informed consent will be obtained at the beginning of this visit (see Section I.b. Informed Consent for details). Given current patient volumes, we anticipate recruiting 1-2 women per week over a period of 3-4 months. As the study timeline is brief, 20

participants will be recruited into a MTM treatment group to ensure the feasibility of the intervention approach is tested. If sufficient time remains, an additional 10 participants will be recruited into a usual care comparison condition.

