Anthropometrics: Maternal height, infant weight, and infant length will be collected from the EHR at baseline. Maternal weight will be collected within 2 weeks of delivery, at 2 months, and at 3 months using a digital scale mailed to the participant and facilitated by a member of the study team during the study telephone/virtual visit. In addition to collecting a maternal weight, participants will be provided instructions to weight their infant at the initial post-partum visit. We anticipate that some participants may not want to know their post-partum weight or could experience a negative emotional response to seeing that weight; therefore, participants will be provided with digital scales (BodyTrace) that will transmit weight data via cellular connection. These scales will transmit the data electronically to a digital platform (Carium) that will then provide aggregate data on all study participants to the study team. The display feature of the scale will be covered to prevent either the maternal weight or infant weight being displayed to the participant.

Medical History: Information on history of chronic diseases and other serious health conditions will be collected from the EHR in order to implement the eligibility criteria. Additionally, we will ask participants about their diagnosis of GDM during the current pregnancy, the strategies they may have employed to manage GDM, and their past pregnancy history.

Home environment: Participating women will complete the Confusion, Hubbub, and Order Scale (CHAOS). The CHAOS measure includes 15 items and is designed to capture environmental confusion in the home. In addition, participants will be asked to answer a series of questions about financial stress and food insecurity.

Dietary Habits and Quality: We will evaluate diet quality and dietary habits using a short, validated questionnaire, the Rapid Eating and Activity Assessment for Participants Short Version (REAP-S). The REAP-S was originally developed as a tool for primary care to providers rapidly assess and discuss nutrition and physical activity patterns with patients and consists of 16 questions and designed to focus making it more practical for use with low-literacy populations in clinical settings. The REAP-S can be used to quickly assess the relative intake of fat, cholesterol, fiber, sugar, and selected food groups.

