### H. Analytical Plan

Since this pilot study is primarily about feasibility, analysis will be limited. We will describe baseline characteristics including demographics and cardiometabolic risk factors by CGM metrics. We will use mixed models with a random subject effect to estimate change in glucose metric variables across follow up with adjustment for demographics and other relevant confounders of dysglycemia. We will assess differences in CGM metric changes between participants receiving the MTM intervention and controls with independent sample t-tests. We will conduct similar analysis for change in weight.

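### The between-group comparison of maternal weight change is an unadjusted t-test, although groups are filled in sequence and the pre-gravid and first postpartum weights needed for adjustment are already available

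*Combined protocol and SAP*

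**What the plan says.** Section II gives the status of the outcome: "The second objective is to explore the preliminary effectiveness of the program, via 3-month changes in CGM markers of dysglycemia (primary"), with "maternal diet quality, maternal weight and infant weight change" among the exploratory measures.

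Section III.G (Anthropometrics) gives the timing: "Maternal weight will be collected within 2 weeks of delivery, at 2 months, and at 3 months using a digital scale".

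Section III.H gives the whole weight analysis in one sentence: "We will conduct similar analysis for change in weight". The analysis it copies is the one for the glucose metrics. That is a mixed model adjusted for demographics and other confounders of dysglycemia, and an independent-samples t-test on change between MTM and control participants. No reference weight for change is named.

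Section III.E fills 20 MTM places first and a further 10 comparison places only if time allows. It describes no randomisation. The same section puts "pre-gravid height and weight (to calculate BMI), current weight, diagnosis of GDM, and OGTT results" in the weekly screening dataset; BMI is the only stated use of the pre-gravid weight.

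The Inclusion Criteria accept a pre-pregnancy BMI of 25 or more with no minimum gain. Section I gives the rationale: "the urgent need for successful interventions to reverse maternal weight gain and promote normoglycemia", and "Postpartum dysglycemia & weight retention pose both an opportunity and a challenge".

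**The concern.** A t-test on change relies on the groups being alike in whatever drives postpartum loss. Gestational gain is an obvious driver, because a woman who gained more has more to lose. Here nothing in the design protects balance in gain: the groups are recruited in sequence, they are small, and eligibility leaves gain wide open. The extract in Section III.E and the purpose in Section II both refer to excessive gain, but even that would set a floor and no ceiling. Part of any difference in weight change could then reflect gain before enrolment and not the meals, and the estimate carries variation that available weights could remove.

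A separate, smaller gap is that the rationale concerns retained weight, while change alone cannot show how much is retained. Two women who each lose 5 kg score the same even if one is back at her pre-gravid weight and the other is 10 kg above it. Section III.D says the pilot's estimates will be used to design the full trial, so both points bear on what is carried forward.

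**Working it through.** The plan states no SD, effect size or power for weight, so there is no figure of its own to reproduce.

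**Inputs from the documents.** 20 MTM and 10 comparison women, the latter only if time allows (Section III.E).

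**Assumed inputs, not in the documents.** SD of gain S = 4 or 6 kg; fraction of gain still present at 3 months f = 0.4, 0.6 or 0.8; other 3-month SD 3.5 kg; noise in the first weighing SD 2 kg; for illustration, a 3 kg difference in mean gain between groups.

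**Model.** First postpartum weight W0 = Wpre + G + noise. Three-month weight W3 = Wpre + f·G + error. G is the gain still carried just after delivery; a constant loss at delivery cancels.

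**1. Within a woman.** (W3 − Wpre) − (W0 − Wpre) = W3 − W0. Change in weight is change in retained weight, so gain matters for bias only through a difference between groups.

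**2. Chance imbalance in gain.** The factor is √(1/20 + 1/10) = 0.387. The SE of the group difference in gain is 0.387 × 4 = 1.55 kg to 0.387 × 6 = 2.32 kg. A 3 kg imbalance is 3/1.55 = 1.9 to 3/2.32 = 1.3 of these SEs, before any systematic difference.

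**3. SE of the group difference.**
- Unadjusted change: 0.387 × √[(1−f)²S² + 3.5² + 2²].
- Adjusted for Wpre and W0: 0.387 × √[3.5² + f²S²·4/(S²+4)] × √(27/25). The last factor (1.04) is the cost of estimating two covariates with 30 women.

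**4. Shift from a 3 kg imbalance.**
- Unadjusted change: −(1−f) × 3.
- Adjusted: 3f × 4/(S²+4), the residue left by noise in the first weighing.
- Retained weight (W3 − Wpre) compared without adjustment: 3f.

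| f | S (kg) | SE unadj. | SE adj. | Shift, unadj. change | Shift, adj. | Shift, unadj. retained weight |
|---|---|---|---|---|---|---|
| 0.4 | 4 | 1.82 | 1.44 | −1.8 | +0.24 | +1.2 |
| 0.4 | 6 | 2.09 | 1.44 | −1.8 | +0.12 | +1.2 |
| 0.6 | 4 | 1.68 | 1.47 | −1.2 | +0.36 | +1.8 |
| 0.6 | 6 | 1.82 | 1.48 | −1.2 | +0.18 | +1.8 |
| 0.8 | 4 | 1.59 | 1.52 | −0.6 | +0.48 | +2.4 |
| 0.8 | 6 | 1.63 | 1.54 | −0.6 | +0.24 | +2.4 |

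Monte Carlo checks of the same model agree within about 0.05 kg. The SE falls by about 5% at f = 0.8, S = 4 and by 31% at f = 0.4, S = 6 (1 − 1.44/2.09).

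**5. Recall error in pre-gravid weight, SD 2 kg.** At f = 0.8, S = 4, the best weight on W0 is b = (fS²+4)/(S²+8) = 16.8/24 = 0.7. The added variance is (0.8−0.7)²·16 + 4·0.3² + 4·0.7² = 2.48, so the SE is 0.387 × √(12.25+2.48) × 1.04 = 1.54. The gain is then about 3%; simulation puts it as low as about 1%. At f = 0.4, S = 6 it is still about 27–28%.

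**6. Choice of outcome.** With Wpre and W0 both in the model, replacing W3 by W3 − W0 or W3 − Wpre only changes the coefficients of those covariates by 1. The group coefficient is identical. The benefit comes from the covariates and not from redefining the outcome.

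**The case against.** The strongest reply is that this is an exploratory outcome in a feasibility pilot that disclaims power for any outcome and says its analysis will be limited. Change is what the objective asks for. The largest shift in the table, 1.8 kg, occurs where the unadjusted SE is 1.82–2.09 kg, a 95% half-width of about 3.6–4.1 kg (1.96 × SE), so an exploratory conclusion would seldom turn on it. The size also depends on assumed inputs. All of that stands, and it limits how much weight the point can bear.

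A reader might infer more than the documents support:

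- **That the pilot misses its stated purpose for weight.** Reversing gestational gain is a need stated in the background. It is not a listed objective.
- **That change is confounded by each woman's gain as such.** Pre-gravid weight cancels within a woman. Bias needs a difference in gain between groups, a link between gain and loss, and an enrolled comparison group.
- **That retained weight should replace change as the compared outcome.** Compared without adjustment it is shifted by +1.2 to +2.4 kg in the same settings, which is worse than change at f = 0.6 and 0.8.
- **That adjustment for gain is ruled out everywhere.** The mixed model allows other relevant confounders, although of dysglycemia, so there it is unspecified. Only the t-test plainly has no covariates.

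On the other side, the inclusion criterion on accepting either assignment might suggest random allocation, but no section describes any.

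**Conclusion.** The point holds for the between-group weight comparison. An unadjusted t-test is the stated method, balance in gestational gain is not protected by the design, and a better estimate is available from weights already held or planned. Under the assumed inputs, the SE is about 1.6–2.1 kg unadjusted v 1.4–1.55 kg adjusted, and a 3 kg imbalance in gain moves the result by −0.6 to −1.8 kg v 0.1–0.5 kg. The benefit is large when much of the gain is lost by 3 months. It is slight when most is retained: at 80% retention and a gain SD of 4 kg, precision improves by about 5% (about 1–3% with recall error) and the shift goes only from −0.6 to +0.48 kg.

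The missing estimate of retained weight is a descriptive gap against the rationale, not an error in the outcome. If no comparison group is enrolled, only that part applies. Overall this is a modest improvement to an exploratory outcome.

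**What to change.** In Section III.H:

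1. For weight, replace the t-test with a linear model for 3-month weight with group, pre-gravid weight and first postpartum scale weight as covariates. Report the group estimate with its 95% CI.
2. Name the first postpartum scale weight as the reference for change. At present this is only implied by Sections II and III.G, and the baseline visit in Section III.E may fall before delivery.
3. Report 3-month weight minus pre-gravid weight, with a CI, as a descriptive outcome, and add it to the exploratory list in Section II. Do not compare it between groups without adjustment.
4. State that if the comparison group is not enrolled, only item 3 and the description of change apply.

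The cost is protocol wording, one model, and keeping the screening weights for enrolled women; no new data are collected. The drawbacks are two covariates in a model of at most 30 women, already counted in the adjusted SEs above, and a pre-gravid weight in the health record that may be recalled and not measured.

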### D. Sample Size

We anticipate recruiting a sample of 30 women (12 African-American, 10 Hispanic, 8 Non-Hispanic White). This is a pilot study and is not powered to test the effect of the MTM intervention on any outcome. The

estimates obtained in this study will be used to design a fully powered randomized controlled trial assessing the effect of a post-partum MTM intervention on blood glucose. Estimates of retention and adherence will be used to modify the sample size to account for dropouts and poor adherence. Estimates of the participation and accrual rates will be used to judge the feasibility of the subsequent trial given the required sample size relative to patient availability and our ability to recruit them into our trial.

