### BMI 50+ - 2000 kcal daily

- Breakfast 200-300 kcal
- Mid-morning snack: 200 kcal
- Lunch (provided most days) 450-600 kcal
- Mid-Afternoon snack (on own) 200 kcal

- Dinner (provided most days) 450-600 kcal
- After-dinner snack: 200 kcal

As described previously, study staff will run weekly EHR reports to identify when a participant is admitted to the hospital for delivery. About one week post-EDD, a member of the study team will contact the participant via text or phone call to ensure that she has delivered and is still planning to participate. We will coordinate with the participant and/or other household member to initiate home delivery of MTMs within 2 weeks (14 days) of delivery.

			Visit	
Primary Measures or Constructs	Screening	Baseline	Intervention	Follow-Up
Study evaluation of acceptability				х
Process measures				х
CGM		Х		х
Secondary Measures of Constructs				
Maternal and infant anthropometrics		х	х	х
Rapid Eating Assessment for Participants (REAP-S)		х		х
Food Insecurity		х		х
Awareness of GDM, management		х		
Diet-related comorbidities	х			
Infant feeding plans and practice		х		х
Financial stress		х		
Overall stress		х		
Confusion Hubub and Order Scale (CHAOS)		х		
Plans for weight-loss		х		
Health literacy		х	х	
Social support		Х		х
Data collection for recruitment and retention				
Pregnancy, delivery history		X		
OGTT	X			
Demographics		X		

Once per week, for a period of 3 months, 10 MTM (5 lunches and 5 dinners) portioned to feed one adult and frozen for ease of storage will be delivered directly to the participant's home by Providence Kitchen staff. MTM deliveries will include reheating instructions and recipe cards with nutritional information. During the monthly phone visits with a member of the study team, participants in the MTM treatment group will also be given the opportunity to provide feedback on the weekly meal delivery, food preparation, and troubleshoot any potential issues with this component of the intervention.

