Overall Stress: We will use the Stress Overload Scale-Short (SOS-S), a self-report measure that has demonstrated accuracy in identifying people who will develop stress-related pathology in the wake of stressful experiences. The SOS-S is also frequently used as a viable diagnostic tool for stress and stress-related disorders across diverse populations in the clinical setting.

Plans for Weight-Loss: We will collect a series of questions on satisfaction with weight-status, plans to lose weight post-partum, motivation level for weight-loss, and self-efficacy for weight-loss at baseline for all participants.

Health Literacy: We plan to use a series of single-item questions to assess confidence in filling out medical forms, frequency with which participants need help to read health information, and to rate their own reading ability. These questions have been validated for identifying patients with inadequate and marginal literacy in healthcare settings with limited time for administration.

We will also administer the Newest Vital Sign (NVS) to participating women as part of the monthly phone visit in month 2. The NVS is based on a nutrition label from an ice cream container and is designed to gauge ability to understand food labeling and nutrition literacy. Women will be provided the label via mail or email prior to the visit then asked 6 questions about it.

Social Support: We plan to collect the Lubben Social Network Scale (LSNS-6) to assess social support in study participants at both baseline and 3-months post-partum. Originally developed as a measure of social isolation in seniors, this measure has been previously validated in post-partum populations.

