#### I. Data Management

Case report forms and interviewer-administered questionnaires will be collected on paper and will be reviewed for completeness and accuracy in real time by the study staff during the visit. These forms will then be data entered by the study team member. Participant self-administered questionnaires will be emailed directly to the participant for completion prior to each data collection visit. We will use the Research Electronic Data Capture (REDCap) system for secure, web-based data entry and management. Use of the REDCap system allows real-time monitoring and reporting of study accrual, data collection, and retention rates. If needed, data can be securely downloaded directly by study team members for use in analyses. All data will reside securely within REDCap, and will not be linked to any other servers or analytic programs.

Electronic data are managed centrally, with a feedback mechanism through e-mail and web-based reporting. After reviewing forms for gross errors and missing data, study staff enters data from case report forms and interviewer-administered questionnaires through a web browser. No electronic data are housed locally, but automated data reports are available for the staff to request on-line. Validation checks are applied during the data entry process. These checks include intra- and inter-form checks for consistency of responses, range checking, and checks for required fields and skip patterns.

Participants will be enrolled and assigned IDs through the REDCap interface. Once inclusion and exclusion criteria are verified and the informed consent is completed, study staff will enroll participants and receive IDs immediately. Data collection and participant status will be tracked with a web-based interface.

The REDCap data management system will also provide confidentiality and data security. A very high level of data encryption during transmission (128 bit) coupled with the use of IDs, rather than subject names, provides adequate data security. The use of text containing identifying information is avoided.

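### Financial and overall stress are named as effectiveness outcomes but scheduled only at Baseline; adherence, meant to inform the next trial's sample size, is undefined, and no described measure counts study meals eaten

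*Combined protocol and SAP*

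**What the plan says.** **Stress outcomes.** The second objective in Section II is preliminary effectiveness, framed by 3-month changes in CGM markers. Its exploratory outcomes include "household food insecurity, and validated measures of financial and overall stress (exploratory". The table of measures by visit, printed in Section III.F.a after the calorie plans, has columns for Screening, Baseline, Intervention and Follow-Up. Its rows "Financial stress" and "Overall stress" each carry one mark, under Baseline.

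Section III.G describes both measures without a time point:
- Financial stress: "participants will be asked to answer a series of questions about financial stress and food insecurity".
- Overall stress: "We will use the Stress Overload Scale-Short (SOS-S), a self-report measure".
- By contrast, the social support scale is to be used "to assess social support in study participants at both baseline and 3-months post-partum".

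**Adherence.** Section III.D states: "Estimates of retention and adherence will be used to modify the sample size to account for dropouts and poor adherence". No section defines adherence. The process measures in Section III.G are meals delivered, preparation and delivery costs, delivery problems, nutritional content, videos watched, phone visits completed and days of CGM wear.

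**The concern.** Staff collect what the visit table tells them to collect. If they follow it, no stress value will exist after the intervention, and the pilot cannot report change or a between-group contrast for two outcomes it names. This cannot be repaired once follow-up has closed.

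The adherence gap bears on a stated purpose of the pilot. Whoever plans the next trial would have to choose a definition after seeing the data. For the meals, which Section III.F makes the main intervention component, the only count available would show what reached the home, not what the woman ate. If that count stands in for adherence, the allowance for poor adherence may be too small.

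**Working it through.** **1. Outcomes in the second objective against the visit table**

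| Outcome | Baseline | Follow-Up |
|---|---|---|
| CGM metrics | yes | yes |
| Diet quality (REAP-S) | yes | yes |
| Maternal weight | yes | yes |
| Infant weight (row shared with maternal) | yes | yes |
| Infant feeding | yes | yes |
| Food insecurity | yes | yes |
| Financial stress | yes | no |
| Overall stress | yes | no |

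Six of eight have a Follow-Up mark and two do not. The infant-weight mark is itself open to question: the anthropometrics text in Section III.G describes weighing the infant at the initial post-partum visit, while the shared row is marked at Baseline, Intervention and Follow-Up.

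*Could the columns have been misread?* Two rows can be checked against Section III.G. Social support is marked at Baseline and Follow-Up, which matches the text. Health literacy is marked at Baseline and Intervention, which fits the Newest Vital Sign at the month 2 call. An extraction fault is therefore unlikely. Section III.G also presents financial stress and food insecurity as one series of questions, yet the table repeats only food insecurity.

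**2. Does any described source count study meals eaten?**
- Process measures: meals delivered, not eaten.
- CGM diary: start times only, on CGM wear days only; the Appendix C form does not identify study meals.
- REAP-S: general diet.
- Monthly calls: open feedback on meal delivery and preparation.
- Exit evaluation: satisfaction.

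None does.

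**3. Gap between delivered and eaten**

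Inputs: 20 women in the meal group (Section III.E); 10 meals × 12 weeks = 120 meals each (Section III.F.a). Planned meals: 20 × 120 = 2,400. Assume all are delivered and the woman eats 60–80% herself. Meals counted but not eaten by her:
- at 80%: 0.20 × 2,400 = 480
- at 60%: 0.40 × 2,400 = 960

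**4. What that could do to the next trial**

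The plan gives no effect size, SD, alpha or power, so there is no figure of its own to reproduce. For illustration, assume a full-adherence effect of 0.5 SD, two-sided alpha 0.05, 80% power, 1:1 allocation, and an effect proportional to the share eaten, *a*:

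n per arm = 2 × (1.960 + 0.842)² / (0.5*a*)²

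- *a* = 1.0: 63
- *a* = 0.8: 99
- *a* = 0.6: 175

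Reading full delivery as full adherence when 60–80% is eaten would understate the sample size by a factor of 1/0.8² = 1.56 to 1/0.6² = 2.78.

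**5. What one question per monthly call would give**

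Table 1 places the calls at weeks 4, 8 and 12. Reports: up to 20 × 3 = 60. Coverage per woman: 3 × 10 = 30 of 120 meals, or 25%. With an assumed between-woman SD of 0.20–0.30 in the share eaten, the 95% CI half-width is t(0.975, 19) × SD / √20:
- SD 0.20: 2.093 × 0.20 / 4.472 = 0.094
- SD 0.30: 2.093 × 0.30 / 4.472 = 0.140

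The mean share is estimated to within about ±9 to ±14 percentage points if all 20 women report.

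**The case against.** The stress measures are exploratory in a pilot that Section III.D says is not powered for any outcome. Section III.H limits the analysis and names only CGM metrics and weight, and the usual-care group is recruited only if time allows (Section III.E). In the table the stress rows sit near other Baseline-only rows, such as CHAOS and plans for weight loss, so baseline description may be all that was intended. On meals, the stated purpose is the feasibility of providing them, which a delivery count serves. The call and exit forms appear only in outline and Figure 1 is not available, so a question on intake cannot be ruled out. The meal and sample-size figures rest on assumptions, and the proposed count is self-reported for a quarter of the weeks.

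Much of this is fair. No primary or feasibility result changes. If baseline description was intended, the correction is to the wording of Section II. Adding Follow-Up marks also leaves stress without a stated analysis, because Section III.H has none. But low power concerns how precisely an outcome is estimated; here there would be no later value to estimate from. And measuring delivery for feasibility does not supply the adherence estimate that Section III.D promises.

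**Conclusion.** Both parts hold. As scheduled, two of the eight outcomes in the second objective have no post-intervention value, so only their baseline levels can be described. Adherence has a stated use but no definition, and no described measure counts study meals eaten; delivered meals give an upper bound only.

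The scheduling finding rests on the documents alone, with the column reading supported by two rows that the text confirms. The 480 to 960 meals depend on the assumed 60–80% eaten with full delivery. The sample-size factors of 1.56 to 2.78 depend further on an effect proportional to meals eaten. The ±9 to ±14 points depend on the assumed SD and on all 20 women reporting, and do not allow for reporting bias. This should be corrected; it does not undermine the pilot's feasibility aims.

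**What to change.** 1. Mark the financial stress items and the SOS-S at Follow-Up in the visit table and send them with the other 3-month forms. Section III.I already provides the route: "Participant self-administered questionnaires will be emailed directly to the participant for completion prior to each data collection visit". Add a line to Section III.H saying how stress change will be summarised. If only baseline description is intended, remove both from the effectiveness list in Section II instead.
2. Add one question to each monthly call in the meal group (weeks 4, 8 and 12), asking how many of last week's 10 study meals the participant ate herself. Define meal adherence in Section III.D as the mean share eaten from these reports, and report meals delivered separately as feasibility.
3. State in the anthropometrics text of Section III.G when infants are weighed, so that it agrees with the table.

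The cost is two short forms, one question in an existing call and a few minutes of participant time. The meal count rests on self-report for 3 of 12 weeks and may overstate consumption, so it should be reported with that limit and with the number of women answering.
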